Written consent will be acquired by patients before initiation of the research study. Research nurses or research coordinators, who are not involved in the intervention or in clinical patient care will administer the questionnaire packets preoperatively (in TCI) and after the last Reiki treatment or usual care day of the research intervention for the following data: anxiety and depression and sleep. After preoperative data collection, patients will be randomized to the usual care or intervention group: using envelopes with assignments (136 control subjects 136 experimental subjects); based on groups of 20. Packets will be created by a nurse from the Office of Research and Innovation and envelope assignments will not be shared with any researcher. Research nurses or research coordinators can assist patients with completion of baseline and post-intervention questionnaires, as desired.

Data retrieved from administrative, EPIC and cardiothoracic surgery databases will be requested using usual procedures, after patients have completed the study. The cardiothoracic surgery database is IRB approved.

Sample Size

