Depression and anxiety are the primary outcomes. In a study of healing touch among hospital patients recovering from cardiac surgery (MacIntyre et al, 2008), those who received healing touch had a 71% greater change in “anxiety” score, compared to control subjects (mean decreases: healing touch, 6.3 [2.0, 10.6] and control group, 1.8 [-2.6, 6.2], $p=0.01$). For this research study, we are hypothesizing that Reiki and manual therapy will result in a *30% greater reduction of depression and anxiety* compared to patients in the usual care group. A rate of 30% was selected based on previous research findings: In a cohort of patients who received surgical procedures, postoperative anxiety BSI had a mean of 0.51 and a standard deviation of 0.56, and depression BSI had a mean of 0.42 and a standard deviation of 0.56 (Mackay, Hansen, & McFarlane, 2004). Given the skewed nature of these data, a lognormal distribution was assumed, with a coefficient of variation (standard deviation/mean) of 1.35, based on the depression BSI results above. We believe that a 30% reduction in mean depression and anxiety scores would be clinically important. Based on use of a two-sided two-sample t-test with significance level of 0.05, with adjustment for use of analysis of covariance based on an assumed small positive correlation between baseline and follow-up ($\rho=0.25$) as described by Borm et al. (2007), a sample size of 123 per group would provide 80% power to detect this difference. To account for loss-to-follow-up, recruitment was increased by 10%, creating a sample size of 136 patients per group (272 patients in total). Sample size calculations were performed using SAS software (version 9.4; Cary, NC) by [name] MS of QHS.

Data Analysis

Patient characteristics will be summarized using frequencies and percentages for categorical measures, and means and standard deviations or medians and quartiles, as dictated by the distribution of these measures.

Anxiety, depression and sleep analyses: an analysis of covariance models will be fit, using the follow-up score as the response and patient group and baseline levels of the outcome measure as predictors by using the Brief Symptom Inventory (BSI).

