Pain, LOS and other continuous factors: will be compared between groups using analysis of variance models. In each of the models, normality of the outcomes will be evaluated and, if necessary, data will be transformed prior to analysis. Results will be back-transformed for presentation of mean differences with 95% confidence intervals.

Reduced new onset of atrial fibrillation and reduced 30-day hospital readmission are binary outcomes that will be evaluated using Pearson chi-square tests or Fisher exact tests, in the case of rare outcomes.

Exploratory analyses will evaluate the relationship between patient characteristics and outcomes and adjust treatment group differences for these factors using similar methodology. An analysis will be performed using SAS software (version 9.4; Cary, NC). A significance level of 0.05 will be assumed for all outcomes.

Feasibility

The facility has sufficient trained Reiki certified practitioners to provide these modalities safely and accommodate the sample size. Hand placements and manual therapy specific for this study will be conducive for this patient population and will not put the patient at risk. The facility does at least ten cardiac surgeries Monday through Friday specific for this study to meet criteria for sample size.

Limitations and Anticipated Problems

Patients may be off the floor, busy with another service, sleeping or too sick (worsening status, readmitted to the ICU, intubated and sedated) or nauseated to be approached to carry out the Reiki intervention, even after enrollment. Not all patients will receive 3 sessions. To make up for possible attrition, 10% will be added to the minimum sample size. Patients may refuse therapy (a rare occurrence) or may not complete questionnaire tools. Administrative and cardiovascular registry data will be used to collect most variables. If there is a delay in data collection or entry into the database, we may be delayed with analysis.

Human Subjects Protection

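### Expected missed sessions are answered with the 10% meant for loss to follow-up; keep those patients in follow-up and state what delivery the 30% effect assumes

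*Combined protocol and SAP*

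**What the plan says.** The Sample Size section powers the trial on depression and anxiety, measured with the Brief Symptom Inventory: "a sample size of 123 per group would provide 80% power to detect this difference". The difference is a 30% lower mean score, justified as clinically important. The 10% allowance is then explained: "To account for loss-to-follow-up, recruitment was increased by 10%, creating a sample size of 136 patients per group".

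The Limitations and Anticipated Problems section lists reasons why the intervention may not be delivered after enrolment: the patient is off the floor, with another service, asleep, nauseated or too sick. It continues: "Not all patients will receive 3 sessions. To make up for possible attrition, 10% will be added to the minimum sample size". It then adds that patients may occasionally refuse therapy or leave questionnaires incomplete.

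Three other places bear on what happens to such patients:

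- **Data Collection Procedures** times the follow-up questionnaires from the last Reiki treatment in the intervention arm and from the last usual-care day in the control arm. Database outcomes "will be requested using usual procedures, after patients have completed the study".
- **Exclusion criteria** lists prolonged intubation and tube reinsertion as leading to withdrawal from the intervention.
- **Data Analysis** specifies analysis of covariance but names no analysis population and does not mention patients with fewer than three sessions.

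**The concern.** Loss to follow-up and missed sessions act on different parts of the power calculation. A patient with no follow-up score reduces the number analysed, which a recruitment margin replaces. A patient who misses sessions but completes the questionnaire stays in the comparison and may pull the average treatment effect towards zero. One 10% allowance cannot fully serve both purposes.

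The more serious risk is selection. The listed reasons for non-delivery include worsening status, return to intensive care and intubation. If these patients count as attrition, they leave mainly from the intervention arm, because the section is about approaching patients to give Reiki. The questionnaire timing points the same way: an intervention patient with no session has no last treatment from which to time the follow-up, whereas a control patient has a defined day. Losing sicker patients from one arm would favour the intervention on mood. If the exclusion extended to the database outcomes, it would also favour it on length of stay, atrial fibrillation and readmission.

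**Working it through.** **Inputs (Sample Size section).** Two-sided t-test at 0.05; ratio of means 0.70; "a lognormal distribution was assumed, with a coefficient of variation (standard deviation/mean) of 1.35"; baseline to follow-up correlation 0.25.

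**Reproducing the plan.**
- Log-scale SD = sqrt(ln(1 + 1.35²)) = 1.0186.
- Log-scale difference = ln(0.70) = -0.357.
- Covariance-adjustment factor = 1 - 0.25² = 0.9375.
- The unadjusted t-test needs 130 per group, and 130 × 0.9375 = 121.9, so 122. The plan's 123 agrees closely, and power at 123 is 80.6%.
- 123 × 1.10 = 135.3, so 136.

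**Reserve.** After 10% loss, 136 × 0.90 = 122.4 per group remain. Holding 80% power then needs 99.4% of the full effect, so there is almost no margin for anything else.

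**Dilution if 30% is the full three-session effect.** Let f be the share of the effect retained on average across the intervention arm. The documents give no value, so f is an assumption. Two versions were computed: dilution on the log scale, difference = f × ln(0.70), and dilution of the mean, difference = ln(1 - 0.30f).

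| Dilution (1 - f) | Power, 123 per group (log / mean) | Power, 136 per group, no loss (log / mean) |
|---|---|---|
| 0% | 80.6% | 84.4% |
| 5% | 76.5% / 75.7% | 80.6% / 79.8% |
| 10% | 72.0% / 70.3% | 76.3% / 74.6% |
| 20% | 61.8% / 58.5% | 66.2% / 62.8% |

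A 10% dilution does not need patients with no sessions at all. If 30% of patients miss one of three sessions and benefit is proportional to sessions (both assumptions), dilution is 0.30 × 1/3 = 10%.

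**What the margin can absorb.** With no loss at all, 136 per group keeps 80% power down to f = 0.943 on the log scale, a dilution of 5.7%. On the mean scale, 1 - 0.70^0.943 = 0.286 and 0.286/0.30 = 0.952, a dilution of 4.8%. Hence about 5-6%.

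**Selective loss.** Suppose there is no treatment effect, 10% of the intervention arm is dropped, and their log scores lie 0.5 SD above those of the patients who stay (all assumptions). The intervention arm's log mean falls by 0.10 × 0.5 × 1.0186 = 0.051, and the ratio of geometric means becomes exp(-0.051) = 0.95 instead of 1. This ignores baseline adjustment, which at a correlation of 0.25 would remove little.

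**The case against.** The best defence is that the plan's power statement is correct as written: 123 per group does give 80% power for a true 30% reduction. A reader might infer that the stated power is wrong. The documents do not support that, because they never say whether 30% is the effect of three delivered sessions or the average effect with delivery as expected. If it is the latter, nothing is lost by keeping under-treated patients.

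Other parts of the defence also stand:

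- The Limitations section says attrition. That the 10% is meant to answer missed sessions is inferred from adjacent sentences, although it is the natural reading.
- Extra patients can offset dilution: at 10% dilution, power is higher with 136 than with 123 per group. The difficulty is that these patients are already committed to replacing losses.
- Some patients who miss sessions, such as those intubated and sedated, will be unable to complete a questionnaire and are genuine losses.
- Controls have a protected rest period that can also be interrupted, so imperfect delivery is not confined to one arm.
- Nothing says that partly treated patients will be dropped. Most variables come from administrative and registry data, and the sentence on requesting those data concerns timing, so it is weak evidence of exclusion.

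The defence does not remove the gap. The plan expects missed sessions, offers only the loss-to-follow-up margin in reply, and ties the intervention arm's follow-up to a treatment that some patients may not receive.

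**Conclusion.** The concern holds in conditional form. The plan does not say whether patients with missed sessions are kept, and each course needs something it does not supply. If they are treated as attrition, or missed because the questionnaire has no anchor, sicker patients may be lost mainly from the intervention arm. If they are kept, the 80% rests on an unstated condition: that 30% is the average effect under expected delivery. If 30% is the full-delivery effect, power at 123 per group is about 76% with 5% dilution and 70-72% with 10%.

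The dilution levels, the 10% one-arm drop and the 0.5 SD gap are assumptions. They show scale and are not forecasts. A reader might conclude that the trial is underpowered or that biased exclusion is planned; the documents establish neither. What they show is an avoidable route to selective loss, which can be closed at almost no cost before the data are analysed.

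**What to change.** 1. **Limitations and Anticipated Problems:** say that the 10% covers missing follow-up questionnaires only, and that missed sessions are not attrition.
2. **Data Collection Procedures and Data Analysis:** say that every randomised patient, including those with 0, 1 or 2 sessions, is given the follow-up questionnaires on the same fixed study day in both arms where able, has database outcomes pulled, and is analysed in the randomised group. Define that day without reference to the last session received.
3. **Exclusion criteria:** reconcile the withdrawal wording with item 2, so that it is clear whether a patient withdrawn from the intervention remains in follow-up and analysis. Human Subjects Protection also places the questionnaires after a fourth session although the intervention has three; these passages must be reconciled too.
4. **Sample Size:** keep 272 patients. State that 80% power assumes 30% is the average effect across all intervention patients as delivered, and add a short sensitivity range labelled as assumption, for example 5% and 10% dilution.

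The cost is minor rewording and a slightly less favourable, conditional power statement. No patients or sessions are added.
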